Based on results obtained in different CMT animal models, the exposure (AUC_{0-24h}) for optimal efficacy is estimated between 19.89 and 43.18 ng/ml.h and C_{max} for 2 administrations per day in the range of 2.5 to 3.89 ng/ml (Table 7). According to the pharmacokinetics results from the SAD in healthy volunteers, the three following doses of 15, 30 and 50 mg daily cover to the range of optimal efficacy (exposure between 12.82 and 42.62 ng/ml.h, C_{max} between 1.20 and 3.77 ng/ml). The escalating ratio is 2 between the low and middle doses and 1.66 between the middle and high doses. To conclude, the maximal ascending dose will be 50 mg daily (2 x 25 mg) according to the preclinical population pharmacokinetics model and the preliminary pharmacokinetics results of the single day.

Table 8: Predicted mean plasma C_{max} and $AUC(0-inf)$ in humans following 14-day dosing of IFB-088 and associated safety coverage

Daily dose (mg)	Daily administered doses (n x mg)	Escalating dose ratio	Expected Human C_{max} (ng/ml) ⁽¹⁾	Expected Human AUC (0-inf) (ng.hr/ml) ⁽¹⁾	C_{max} safety coverage % of C_{max} in dogs ⁽²⁾	AUC safety coverage % of AUC in dogs ⁽²⁾
15	2 x 7.5	-	1.20	12.82	1.5%	2.5%
30	2 x 15	2	2.26	25.57	2.9%	4.9%
50	2 x 25	1.67	3.77	42.62	4.9%	8.2%
Stopping criteria			23.77	111.14	30.2%	21.5%

(1) Data are extrapolated from pharmacokinetics results of the SAD observed at a daily dose of 60mg (30mg BID), taking into account that IFB-088 C_{max} and AUC are dose-proportional at these dose levels.

(2) Safety coverage is calculated based on C_{max} and AUC_t at NOAEL for the sex with the lowest C_{max} and the lowest AUC_t

Criteria for dose modifications or stopping dose escalation:

The criteria to modify planned doses or stop dose escalation will be the same as the ones used for single ascending dose escalation, as NOAEL in Sprague Dawley rats is maintained and NOAEL in Beagle dogs increased following the results of the 13-week GLP toxicity study, *i.e.*

- $AUC > 111.14$ ng/ml.h, and
- $C_{max} > 23.77$ ng/ml.

Based on the SAD exposure in humans and on the additional toxicity studies performed in animals, the daily doses for the multiple ascending dose to be administered in Humans to cover

the envisioned therapeutic indications (Charcot-Marie-Tooth) and to ensure maximum safety are:

- **15 mg/day given as 2 administrations of 7.5 mg in the first cohort;**
- **30 mg/day given as 2 administrations of 15 mg in the second cohort;**
- **50 mg/day given as 2 administrations of 25 mg in the third cohort.**

1.2.4. *Rationale for Study population*

As is usual in first-in-man studies, the population to be included is healthy young males between 18 and 40 years old (inclusive) at screening. The selection of healthy subjects is justified on the basis that PK, safety, and tolerability, can be investigated accurately in this population.

In this population, the study can be performed under standardized conditions, reducing the influence of confounding factors.

No medical benefit for the subjects can be expected beyond the thorough medical check-up that each subject will receive prior to treatment and at the end of the study. The potential risks associated with IFB-088 are not known, as this product has not yet been tested in humans.

The study protocol is designed to ensure a careful observation and medical management in order to minimize any associated risk in this study.

The participation of healthy subjects in this study is justified with regard to the expected benefit for the target population that will receive this therapy after registration of the compound.

1.3. **Summary of Risk Management**

1.3.1. *Cardiovascular Monitoring*

Since IFB-088 is devoid of alpha-2 adrenergic activity, a potent reduction in blood pressure is not expected with IFB-088. In addition, even if in vitro, in a HERK study IFB-088 was classified as a potential moderate HERK channel inhibitor, IFB-088 at 1, 3 or 9 mg/kg/day (0.5, 1.5, 4.5mg/kg/administration) had no effect on heart rate, systolic, diastolic and mean arterial blood pressure, ECG parameters or body temperature in conscious male beagle dogs and no treatment-related arrhythmias were observed at any of the dose-levels administered in dog (see Investigator Brochure [section 4.1.3.2](#) and [section 4.1.3.5](#)). Nevertheless, as usual in a first in man study a particular attention will be focused on cardiovascular monitoring. Vital signs (systolic and diastolic blood pressure, heart rate) will be closely monitored at regular intervals post dosing, both in supine and standing position and ECG parameters will be controlled at regular intervals post-dosing.

1.3.2. *Drug-induced renal crystals*

Preliminary toxicity studies pointed out renal findings after 10 or 14 days once a day administration from 10 mg/kg in dogs and rats. In particular, intratubular crystals were observed

at the upper dose tested. IFB-088 was localized in the crystals observed in each kidney from each treated animal whereas IFB-139 metabolite was distributed in the entire kidney tissue with the most intense signals localized in the crystals.

In Beagle dogs, twice daily administration for 28 days was well tolerated up to 9mg/kg (NOAEL in this species) without any renal findings suggesting that when administered twice daily IFB-088 is better tolerated than when daily administered.

A twice-daily administration is thus proposed from cohort 2 and an appropriate monitoring plan will be set up with a regular check of renal function parameters (creatinine, urea, estimated Glomerular Filtration Rate and urinary dosage of Beta2 microglobulin, proteins and creatinine), volume of diuresis and urinary parameters by dipstick (pH, hematuria). An increased excretion of beta2microglobulin in the urine is a sensitive indicator of proximal tubular dysfunction (Ostermann M., Joannidis M (2016).

A minimal intake of at least 2L of water post dosing will be mandatory to ensure a sufficient hydration (250 mL with study drug, then 500 mL between dosing and T4H, 1000 mL between T4H and T12H and 500 ml between T12H and T24H).

1.3.3. *Liver monitoring*

Hepatic enzymes are systematically recorded in phase 1 trials but, considering that at the highest dose tested in the 28-day GLP study in rats (9 mg/kg/day SID), an increase of liver enzymes was observed, and that there is a known important hepatic first pass effect for guanabenz, a strategy will be implemented according the FDA guidance (Drug-Induced Liver Injury: Premarketing Clinical Evaluation) to initiate close observation immediately upon detection and confirmation of early signals of possible impairment of liver function (See Section 3.4.3.1 and 8.10).

2. OBJECTIVES AND ENDPOINTS

2.1. Primary objectives
	
End Points

To investigate the safety and tolerability after single and multiple oral doses of IFB-088 in healthy volunteers
	
 - Adverse events - Laboratory parameters (haematology, chemistry, urinalysis) - 12-lead ECG parameters - Vital signs (supine and standing systolic and diastolic blood pressure, pulse rate, tympanic temperature) - Vigilance (Bond and Lader scale)

2.2. Secondary objectives
	
End Points

To investigate the pharmacokinetics after single and multiple oral doses of IFB-088 and its metabolite in healthy volunteers
	
 - Plasma - Peak plasma concentration (C_{max}) - Time of peak plasma concentration (t_{max}) - Area under the plasma concentration-time curve from time-zero to last sample with measurable concentration (AUC_{last}) and from time 0 extrapolated to infinity (AUC_{0-∞}) - Terminal half-life (t_{1/2}) - Apparent total body clearance (CL/F) - Urine - Maximum observed concentration (C_{maxU}) - Time of occurrence of C_{maxU} (t_{maxU}) - Area under concentration-time curve from time-zero to last sample with measurable concentration (AUC_{last}) and from time 0 to infinity (AUC_{0-∞}) - Renal clearance - Total amount excreted in urine (A_e) - Concentration at the end of a dosing interval before the next dose (C_{trough})

2.3. Exploratory objectives
	
End Points

To explore UPR related biomarkers
	
 - Blood samples

3. INVESTIGATIONAL PLAN

Protocol waivers or exemptions are not allowed with the exception of immediate safety concerns. Therefore, adherence to the study design requirements, including those specified in the Time and Events Table, are essential and required for study conduct.

3.1. Study Design

This is a double blind, randomized, placebo-controlled combined SAD and MAD study.

3.1.1. Overview SAD study design

This part of the study will be conducted according to a randomized, double blind, placebo controlled, single oral ascending dose design in 6 independent cohorts of 8 healthy male subjects. If a subject is withdrawn from this study part, the subject may be replaced as necessary with another subject assigned to the same treatment with respect to active and placebo doses at the discretion of the sponsor's team in consultation with the investigator.

Each potential subject will undergo:

- A Screening visit prior to initiation of any study-specific procedures:
 - It can take place up to 21 days before the first dosing session,
 - Informed consent will be obtained prior to any procedure with an assessment of inclusion and exclusion criteria.
- A Treatment Phase:
 - Subjects will be required to join the unit on the day prior to dosing (Day -1) and will be required to stay in the unit for up to 2 nights for the treatment period. Subjects will be dosed on Day 1. A continuous monitoring of adverse events, regular check of vital signs, ECG and diuresis will be set up. PK blood samples and urine samples will be taken for up to 32 h post-morning dose.
 - Vigilance will be assessed at regular intervals by Visual Analogic Scales (VAS) from pre-dose to discharge (Bond Lader).
 - Safety parameters particularly vital signs, in the opinion of the investigator, must have returned to baseline values prior to discharge. Duration of both subject stay and PK sampling may be subject to changes, depending on emerging safety and PK results.
- A Follow-up visit:
 - Subjects will be required to return to the unit for a follow-up visit 7 to 14 days after dosing.

Cohort features:

- It is anticipated that 6 cohorts of 8 subjects will be studied.
- In each cohort, 6 subjects will receive active treatment and 2 will receive placebo.

IFB-088 dosing

- The planned doses of IFB-088 are 2.5 mg, 5, 10, 20, 40 and 60 mg administered as oral capsule.

- The maximum daily predefined dose will be 60 mg.
- The planned dosing schedule may be adjusted to allow administration of intermediate doses if dose-limiting toxicity becomes evident at any dose level or to obtain additional safety, tolerability, or PK data.
- In the first group of each cohort, two (2) subjects will be dosed on Day 1 (one on active treatment and one on placebo). The 6 remaining subjects will be dosed by successive groups of 3 subjects, with an adequate period between groups to observe for any reaction and adverse events (at least 36 hours between last assessment of the subjects and dosing of the following).
- In the first cohort (2.5 mg), dosing will be in the morning under fasting state (see Section 6.6.2)
- From the second cohort, the planned daily dose will be divided into 2 doses separated by an interval of 12 hours (1 dose in the morning fasting and 1 dose in the evening 2 hours before dinner) (See paragraph [1.2.2.1](#)).
- A dose escalation committee (DEC) comprised of members from the sponsor's team and the investigator's team, will be convened prior to the start of each subsequent dosing session to interpret the clinical safety, tolerability, laboratory, and PK exposure, and make a decision to proceed to the next higher dose.
- Data gathered from previous cohort will be available prior to dosing the next cohort in order to carefully monitor each dose level.

3.1.2. *Overview MAD study design*

This part of the study will be conducted according to a randomized, double-blind, placebo controlled, multiple oral ascending dose design in 3 independent cohorts of 8 healthy male subjects.

Each potential subject will undergo:

- A Screening visit prior to initiation of any study-specific procedures:
 - This can take place up to 21 days before the first dosing session,
 - Informed consent will be obtained prior to any procedure with an assessment of inclusion and exclusion criteria
- A Treatment Phase:
 - Subjects will be required to join the unit on the day (Day -1) prior to the first dose and will be required to stay in the unit for 17 days for the treatment period. Subjects will be dosed from Day 1 to Day 14. A continuous monitoring of adverse events, regular check of vital signs, ECG and diuresis will be set up and serial PK blood and urine samples will be collected.
 - Vigilance will be assessed at regular intervals by Visual Analogic Scales (VAS) from pre-dose to discharge (Bond Lader).
- A Follow-up visit:

- Subjects will be required to return to the unit for a follow-up visit 7 to 14 days after last dosing.

Cohort features:

- It is anticipated that 3 cohorts of 8 subjects each will be studied.
- In each dosing session, 6 subjects will receive active treatment and 2 will receive placebo.

IFB-088 dosing

- The planned doses are 15 mg per day (2 x 7.5 mg at 12-hour interval) in cohort 1, 30 mg per day (2 x 15 mg at 12-hour interval) in cohort 2 and 50 mg per day (2 x 25 mg at 12-hour interval) in cohort 3.
- The maximum predefined dose will be 60 mg daily (30 mg twice).
- The planned dosing schedule may be adjusted to allow administration of intermediate doses if dose-limiting toxicity becomes evident at any dose level or to obtain additional safety, tolerability, PK data.
- In the first group of each cohort, two (2) subjects will be dosed on Day 1 (one on active treatment and one on placebo). The 6 remaining subjects will be dosed by successive groups of maximum 3 subjects, with an adequate period between dosing to observe for any reaction and adverse events (*i.e.* at least 36 hours between last assessment of the subjects and dosing of the following, corresponding to at least 5 fold the half-life of the drug according to PK results obtained in the SAD part). This period could be modified on the basis of safety and PK results.
- A dose escalation committee (DEC) comprised of members from the sponsor's team and the investigator's team, will be convened prior to the start of each subsequent dosing session to interpret the clinical safety, tolerability, laboratory, and PK exposure, and make a decision to proceed to the next higher dose.

Data will be available prior to dosing the next cohort in order to carefully monitor each dose level.

3.2. Study endpoints

3.2.1. Safety endpoints

Safety and tolerability parameters evaluated during this study are:

- Clinical safety: adverse event information, prior and concomitant medications, physical examination (including body weight), vital signs, 12-lead ECGs, vigilance (Bond and Lader VAS)
- Laboratory safety assessments: standard hematology, biochemistry analyses, urinalysis, serology, alcohol breath test, urine drug screen.

3.2.2. *Pharmacokinetic end points*

The following parameters for IFB-088 and IFB-139 will be derived, where appropriate:

Plasma:

- Maximum observed plasma concentration (C_{max}),
- Time of occurrence of C_{max} (t_{max}),
- Terminal elimination rate constant (K_{el}),
- Terminal half-life ($t_{1/2}$),
- Area under plasma concentration-time curve from hour 0 to last sample with measurable plasma concentrations (AUC_{last}),
- Area under plasma concentration-time curve from hour 0 to infinity ($AUC_{0-\infty}$),
- Apparent volume of distribution (V_d/F),
- Apparent total body clearance (CL/F),
- Last measurable plasma concentration (C_{last}),
- Time to reach last measurable plasma concentration (T_{last}),
- Concentration at the end of a dosing interval before the next dose administration (C_{trough}),

Urine:

- Maximum observed urine concentration (C_{maxU}),
- Time of occurrence of C_{maxU} (t_{maxU}),
- Area under urine concentration-time curve from hour 0 to last sample with measurable urine concentrations (AUC_{last}),
- Area under urine concentration-time curve from hour 0 to infinity ($AUC_{0-\infty}$),
- Renal clearance (CL_r),
- Total amount excreted in urine (A_e),
- Percent of drug recovered in urine ($A_e \%dose$).

Additional parameters could be calculated if deemed necessary.

3.2.3. *Biomarker assessment (exploratory)*

There is no biological UPR biomarker identified in fluids in healthy subjects.

With the subject's consent, blood samples will be collected during this SAD part of the study and may be used as healthy controls for the purpose of research of UPR biomarkers in patients' populations.

3.3. **Discussion of the Design**

The selected designs for the 2 parts of this study are as follows:

The SAD part consists of 6 cohorts of 8 healthy young male subjects, each receiving a single oral dose of IFB-088 or placebo (6 verum and 2 placebo) administered daily in the morning (cohort 1) or divided into 2 doses, 12h apart (cohort 2 to 6).

In each cohort, 2 subjects (1 verum and 1 placebo) are to be dosed first; if the safety and tolerability results are acceptable after at least 36 hours (48 hours for cohort 1), two groups of 3 subjects will be dosed at least 36 hours apart (48 hours for cohort 1).

The MAD part consists of 3 cohorts of 8 healthy young male subjects, each receiving an oral dose of IFB-088 or placebo (6 verum and 2 placebo) daily for 14 days.

In each cohort, 2 subjects (1 verum and 1 placebo) are to be dosed first and after an adequate period of time to observe for any reaction or adverse event (at least 36h), and if the safety and tolerability results are acceptable, a maximum of 3 subjects will be dosed then a maximum of 3 subjects after at least 24 hours. The 36-hour interval between the administration for the first 2 subjects in a cohort and the remaining subjects have been specified according to the available safety and PK data obtained in the SAD part of the study.

These designs are well-established for first-in-man studies and appropriate to assess the preliminary safety and tolerability of new drug candidate.

For the SAD part, the sample size of 8 subjects per dose level (6 verum and 2 placebo) is deemed adequate for this type of study (Buoen C et al 2003).

For the MAD part, there will be 8 healthy young subjects per dose level (6 verum and 2 placebo). This number is deemed adequate for the objectives of this study part (Buoen C et al 2003).

During this study, safety parameters will be closely followed by regular measurements, to enable a detection of any changes as early as possible and to be able to stop dosing before occurrence of major deleterious effect.

The follow-up observation for the end of study visit will take into account the results of previously available PK parameters (especially for the potential occurrence of delayed AEs) and could be changed if necessary for safety reasons.

The use of placebo as a control is necessary to provide reliable scientific evidence of safety and tolerability and to ensure a reliable evaluation of the tested drug.

A double-blind design is used in conjunction with a placebo control to prevent a potential bias generated by the knowledge of the administered test drug.

The sequential ascending dose design will be used for a safe determination of the maximal exposure in human.

This study design is in line with the current regulatory guidance and appropriate to reach the objectives of the study. (Guideline on strategies to identify and mitigate risks for first-in-human and early clinical trials with investigational medicinal products - EMEA/CHMP/SWP/28367/07 Rev. 1 20 July 2017).

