Study Design	
Randomized, double blind, placebo controlled study of single ascending doses (SAD) and multiple ascending doses (MAD)
 
The SAD part consists of 6 cohorts of 8 healthy young male subjects, each receiving a single oral dose of IFB-088 or placebo (6 verum and 2 placebo). In each cohort, 2 subjects (1 verum and 1 placebo) will be dosed first. If the safety and tolerability results are acceptable, the 6 remaining subjects will be dosed by 2 successive groups of 3 subjects, with an adequate period between the 2 groups to detect the occurrence of any reaction or adverse events, namely at least 48H for the first cohort and at least 36H for the following cohorts. Indeed, in the first cohort (2.5 mg IFB-088 base), dosing will be in the morning only. From the second cohort, the planned daily dose will be divided into 2 doses separated by an interval of 12 hours (1 dose in the morning fasting and 1 dose in the evening 2 hours before dinner).
 
The MAD part consists of 3 cohorts of 8 healthy young male subjects, each receiving an oral dose divided into two doses of IFB-088 or placebo (6 verum and 2 placebo) for 14 days. In each cohort, the 2 first subjects will be dosed on Day 1 (one on active treatment and one on placebo). The 6 remaining subjects will be dosed by 2 successive groups of maximum 3 subjects with an adequate period between the groups to observe for any reaction and adverse events. This period will be of at least 36H, corresponding to at least 5-fold the half-life of the drug (based on results obtained during the SAD part) when steady state will be achieved. In each MAD cohort, the total daily dose will be divided into 2 doses separated by an interval of 12 hours.
		

Number of subjects	Seventy-two (72) healthy young subjects (48 in the SAD part and 24 in the MAD part)												

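### The MAD stagger between dosing groups is stated inconsistently, and counting 36 h from dosing lets group 2 start before any post-dose laboratory result from the sentinels

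*Combined protocol and SAP*

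**What the plan says.** Three places set the MAD stagger.

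- **Section 3.3 (Discussion of the Design).** The second group is dosed after a period "to observe for any reaction or adverse event (at least 36h), and if the safety and tolerability results are acceptable". The text then allows "a maximum of 3 subjects will be dosed then a maximum of 3 subjects after at least 24 hours". It describes the interval as "The 36-hour interval between the administration for the first 2 subjects in a cohort and the remaining subjects", so the clock starts at the sentinels' dose.
- **Section 3.1.2 (Overview MAD study design).** The gap is "at least 36 hours between last assessment of the subjects and dosing of the following, corresponding to at least 5 fold the half-life", and it applies to each successive group. Last assessment is not defined. The same bullet allows the period to be changed in the light of safety and PK results.
- **Synopsis, Study Design.** The six remaining subjects are dosed in "2 successive groups of maximum 3 subjects with an adequate period between the groups", and "This period will be of at least 36H, corresponding to at least 5-fold the half-life of the drug". No start point for the clock is given.

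On data, 3.1.2 makes a commitment between cohorts only: "Data will be available prior to dosing the next cohort in order to carefully monitor each dose level". Section 3.2.1 counts laboratory tests among the safety parameters ("Laboratory safety assessments: standard hematology, biochemistry analyses, urinalysis, serology, alcohol breath test, urine drug screen"), but no section says which sentinel results must be in hand before group 2 is dosed.

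The synopsis (Evaluation criteria) and 6.5.4.3 place the first MAD post-dose safety bloods and urinalysis on D3, before the morning dose. Section 6.5.4.2 lists no safety laboratory test on D2.

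**The concern.** A sentinel step is useful only if staff know when the next subjects may be dosed and what must have been reviewed by then. Here the start of the clock and the length of the second interval both depend on the section followed. The MAD runs at a different centre from the SAD, and section 3 rules out waivers except for immediate safety concerns, so the site needs one rule it can apply.

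The laboratory point is separate. In the SAD, bloods at 24 h and urinalysis at 12, 24 and 32 h all fell inside a 36 h window. The MAD keeps a 36 h window, but its first post-dose laboratory tests come at 48 h. The values that may be missing at release include creatinine and beta-2 microglobulin, chosen to monitor the renal-crystal risk in 1.3.2, and triglycerides, for which 3.4.3.2 adds a stopping rule in the MAD.

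**Working it through.** **1. Is a safety draw planned on D1 or D2?** Section 6.7.2 itemises MAD blood by visit:

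- screening: 18.7 mL
- seven safety draws (D-1, D3, D6, D10, D13, D17, follow-up): 7 x 10.2 = 71.4 mL
- PK: 96 + 32 + 24 + 96 + 56 + 16 = 320 mL

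The total is 18.7 + 71.4 + 320 = 410.1 mL, which reproduces the stated figure. A further draw on D1 or D2 would give 420.3 mL. No post-dose safety blood is therefore planned before D3.

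**2. Earliest starts.** Sentinels are dosed at 08:00 on D1. Section 6.5.4.1 sets doses at 08:00 and 20:00, with the first dose after an overnight fast, so I let a group start only at 08:00. Hours run from the sentinels' first dose.

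| Reading | Group 2 | Group 3 |
|---|---|---|
| 3.3, from administration | 36 h, next slot 48 h (D3) | 48 + 24 = 72 h (D4) |
| Synopsis, if counted from dosing | 36 h, next slot 48 h (D3) | 48 + 36 = 84 h, next slot 96 h (D5) |
| 3.1.2, last assessment = 24 h check | 24 + 36 = 60 h, next slot 72 h (D4) | 96 + 36 = 132 h, next slot 144 h (D7) |

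Other meanings of last assessment move group 2 under 3.1.2 to D3 (12 h check: 12 + 36 = 48 h), D19 (D17 discharge, taken as 08:00) or D23 (earliest follow-up).

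**3. Overlap with the laboratory schedule.** The sentinels' D3 pre-dose sample falls at 48 h. A group 2 start at 48 h is 0 h after it; a start at 72 h is 24 h after it. Group 3 starts no earlier than 72 h on any reading, so it always has at least 24 h after the draw.

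**4. Who is affected.** Section 5.4.1 gives the six later subjects 5 active and 1 placebo, so a group of 3 has at least 2 active. Over three cohorts that is up to 9 subjects, at least 6 of them active.

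**5. The sentinel's dose by then.** Four doses precede D3 08:00 (0, 12, 24 and 36 h): 4 x 7.5 = 30 mg, 4 x 15 = 60 mg and 4 x 25 = 100 mg in cohorts 1 to 3. Totals already followed by laboratory tests are 60 mg in the SAD, 28 x 7.5 = 210 mg after cohort 1 and 28 x 15 = 420 mg after cohort 2. No sentinel total exceeds what came before it.

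**6. The half-life argument.** Five half-lives in 36 h needs a half-life of at most 36/5 = 7.2 h; in 24 h, at most 24/5 = 4.8 h. The SAD half-life is not reported. Table 4's predicted human values give ln 2 x 20.9/9.7 = 1.5 h, but from the central volume only. Whether 24 h also covers five half-lives cannot be verified.

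**7. Does section 3.4.1 close the gap?** It asks for laboratory data to at least 32 h after the last dose before the next group. The last MAD dose is on the evening of D14, so this falls around D16. It can gate the next cohort but not the next group within a cohort.

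**The case against.** - **The intervals are all minima, so the strictest satisfies every section.** This is true of 36 h against 24 h. It does not settle the start point: 3.1.2 gives anything from D3 to D23 depending on what last assessment means. Section 3.3 also tells a reader that 24 h is enough.
- **3.1.2 counted from the 24 h assessments puts group 2 on D4, after the draw.** This stands. A reader might infer that the laboratory gap is a product of 3.3 or of the conflict itself. It is neither: the synopsis counted from dosing permits the same D3 start, and harmonising on 36 h from dosing would leave the gap open.
- **3.3 already demands acceptable safety results, and laboratory tests are among the safety parameters.** Correct in principle, but the condition can be met with no post-dose laboratory value.
- **The laboratory review would rarely trigger a rule.** The cohort rules for creatinine, beta-2 microglobulin, triglycerides and ALT/AST need two subjects. One abnormal value in the only active sentinel could lead to that subject's withdrawal but would not by itself stop the cohort. The gate would mainly inform judgement.
- **The risk is small.** This stands. The top MAD daily dose is 50 mg against 60 mg in the SAD, no accumulation was seen at 24 h, and animal renal findings followed 10 or more days of dosing. SAD triglyceride rises showed no dose relationship and occurred on placebo too. Adverse events, vital signs, ECG and diuresis are available to the person releasing group 2, and tests may be added.

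**Conclusion.** The inconsistency is definite. Section 3.3 gives a shorter stagger than the 36 h, five-half-life rule stated in 3.1.2 and the synopsis, and the start of the clock is either different or undefined.

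The laboratory point holds as a permission. Counted from dosing, group 2 can be released at 48 h with no post-dose laboratory value from the sentinels, for up to 3 subjects per cohort. A reader might infer that the plan requires such a start, or that it exposes subjects to a substantial renal hazard. The documents support neither.

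The timings assume 08:00 fasted starts. Laboratory turnaround is not given. The MAD flow chart (3.5.3) and the DEC charter were not available for this check; the D3 sampling day rests on the synopsis, 6.5.4 and 6.7.2, which agree. Priority is low to moderate.

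**What to change.** State one rule in the synopsis, 3.1.2 and 3.3: at least 36 h from the previous group's first dose, for both the second and the third group. This means replacing the 24 h in 3.3 and deleting or defining last assessment in 3.1.2. Add that group 2 is dosed only after review of the sentinels' D3 pre-dose blood and urine safety results.

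With same-day results, group 2 starts on D4 (72 h) and group 3 on D6 (72 + 36 = 108 h, next slot 120 h). Against 3.3 (D3, D4) that is one day later for group 2 and two for group 3 in each cohort. Against the synopsis (D3, D5) it is one day each. Against 3.1.2 counted from 24 h (D4, D7), group 2 is unchanged and group 3 is a day earlier. No extra sample is needed. Slower laboratory turnaround would lengthen the delay.

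Moving the D3 sample to D2 at 24 h would keep the D3 start, but it is less attractive: the sample would follow two doses instead of four, and the 48 h test would be lost.
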